In the motor impairment domain, secondary outcomes will be increased arm range in pronation/supination (based on new games we developed), grasp strength increase, finger extension range increase, and increase in UEFI. We expect bimanual training to improve CAHAI 9 scores (by at least 6 points), reflecting more ADL independence in tasks that are requiring both arms. The progression in ADL independence will be indicative of transfer to function. Other secondary outcomes will be changes in therapeutic game scores, change in game duration (indicative of reduction in task completion time) and change in play intensity (number of arm movement repetitions/minute). Another secondary outcome will be subjective evaluation scores for ease of use of the BAC, and overall system rating.

In the cognitive domain, we also foresee the subjects will have improved focus, better verbal and visual memory. In the emotional domain, we will evaluate the depression scores as measured by the Becks Depression Inventory II standardized test. We will consider success and average group reduction of 5 points in the severity of depression.

In addition there will be supplementary secondary outcomes:

- a) Scores obtained on the Stroke Impact Scale (Version 3);
- b) feedback from the subjects during the outpatient component of therapy (only for intervention group);
- c) feedback obtained from caregivers during outpatient therapy. The caregivers for subjects in either experimental or control groups will use the same feedback forms and provide feedback at the same time points.

An additional important outcome will be the rate of motor recovery as visualized by the curves of evaluation variables obtained pre-, and post inpatient therapy, then pre-, and post- outpatient therapy. These will provide indication on the envisaged benefits from the use of the experimental device and elucidate what gains are due to natural recovery and what gains may be attributes to training on the BAC.

- o **Data Analysis and Data Monitoring.** We will use repeated measures of ANOVA statistical analysis to look at the participants' data comparing pre-training conventional evaluation results with post-training results, to determine early indications of clinical benefit. We will also collect subjective evaluation questionnaires from each participant and from the occupational therapist (once post-training) on their impression of the system, its perceived benefits and shortcomings, its ease of use in a clinical setting. We will also collect data on Activities of Daily Living, using a standardised form, as well as data from caregivers so to gauge transfer of training to real life activities.

In order to gauge technology acceptance we will collect a subjective evaluation of the BAC from each participant in the experimental group. The scores (1 – least favourable outcome to 5 most favourable one) from each question will be averaged over the group. The BAC subjective evaluation forms will be collected twice (after 6 weeks of outpatient therapy and at end of outpatient therapy). By looking at the progression (or regression) of these scores, we will also be able to determine if ease of use of the technology increased with the accumulation of training sessions (or not).

All the data will be entered to the central data management system remotely.

- o **Data Storage and Confidentiality.** Each subject will have his/her name encoded such that the experimental and clinical measures will not log the participant's real name. The only mapping between the assigned encoded ID and the participant's real identity will be on the consent forms. These will be kept under lock by:

- 1) [name] OT and [name] for the participants early post-stroke PowerBack Rehabilitation;
- 2) [name] for the participants early post-stroke training at Kessler Foundation

The computerized data will be uploaded on a cloud secure database. Access to the database will only be granted to the research team, and will be password protected. Paper records involving the motor and cognitive evaluations as well as the subjective evaluation questionnaires will also be kept locked by [name] OT, [name], [name] (for the cognitive and emotive evaluations of the feasibility subjects) and [name] MD for the controlled trials subjects at Kessler Foundation.

- o **Transition from Research Participation.** Subjects will not have their standard of care or medication interrupted during participation.

iv. **Risk/Benefit Assessment**

- o **Risk Category.** Minimal

- o **Potential Risk.** Potential risks to healthy subjects participating in usability testing BAC or caregivers for CVA survivors will be minimal. For the subjects early post-stroke there may be some chance of muscle or joint soreness from repeated use of arms and hands during interaction with VR training scenes. However, this will be low, as the games will require everyday movements of the arm and hand. Confidentiality of healthy subject information will be protected via use of number codes for subjects, and no specimens will be taken from the subjects.

Data collected for this investigation will be used to determine the feasibility of the *BAC* virtual reality game rehabilitation system in training the arm/shoulder/hand, as well as cognitive functions. Data will include strength, active range of motion, coordination, motor control, spasticity, arm and hand function, memory and focusing, executive function, and quality of life (depression levels). Risks for all subjects during training include sore muscles from arm/hand training, or neck soreness. We anticipate that the frequency will decrease as participants strengthen their shoulder, arm and hand during training. There is also a risk of increased blood pressure during prolonged exposures to virtual reality games. For all subjects blood pressure and pulse rate will be measured before, mid-session and after each training session.

- o **Protection Against Risks.**

Training for subjects at the early post-stroke period will be conducted by trained occupational therapists who are experienced in monitoring exercise levels and handling emergencies.

Since subjects are in the sub-acute stage post-stroke additional measures will be taken:

- a) the session will be shorter;
- b) difficulty of the games with less demanding position of the upper limb by manipulation of table angle;
- c) the mandatory mid-session blood

pressure/pulse measures will also serve as rest break; d) blood pressure and pulse rate will be measured at the start. Mid- and end of each session.

In the unlikely event that a subject should require medical treatment, standard emergency medical procedures will be followed. Occupational therapist in the room during training on the BAC system will assist the stroke survivor participants as needed. In case of muscle soreness we will increase rest periods between games for all participants, and reduce difficulty levels as needed. Participants will always exercise in sitting, for increased balance and safety.

Participants will not be allowed to commence, or continue training if their blood pressure/pulse values are determined to be clinically significant by the treating clinicians. In our experience with BrightArm and with BrightBrainer systems, patients tend to relax, and their blood pressure and pulse rate are actually lower at the end of a session. We observed this reduction in blood pressure both in SNF residents chronic post-stroke and in participants with dementia training on BrightBrainer. The BAC arm support has a wireless transmitter to the PC, used to send grasp strength and finger extension data. We will consult with pacemaker manufacturers to make sure such transmission (433 MHz) does not interfere with a participant's device (if there is one). The HTC VIVE tracker used to measure the patient's hand position and orientation uses low-intensity infrared. We do not believe this will pose a health risk to our subjects.

There is also a risk of emotional discomfort if participants are frustrated with the games (either length, or difficulty, or both). For the participants post-stroke we will shorten sessions, and temporarily reduce difficulty levels, until participants feel more comfortable to be challenged. In our 2010, 2011, 2013, 2014, 2018 trials participants were happier (less depression) post our experimental therapy. The difficulty of the games will be set automatically based on their prior performance, so as to minimize frustration for not winning. Each participant will have an option to choose the games they want to play.

o **Potential Benefits to the Subjects.** The Centers for Disease Control and Prevention (CDC) has reported that 2009 direct and indirect costs associated with stroke totalled 70 billion. This investigation will develop a new product/system that will improve training techniques for the arm/shoulder/grasp for elderly patients early post-stroke when they have weak arms. The system will provide safe, but intensive training, prone to induce substantially more arm repetitions than conventional care. As such we will better take advantage of a period when the brain has highest plasticity for recovery. The investigation further aims to improve the cognitive/emotive state for stroke survivors.

It is well understood in medical practice, and especially in integrative medicine, that patient morale has a positive effect on health. Our system will keep morale high by enabling participants to win, and by rewarding them through applause, and congratulatory text on the game screen. Participants in the feasibility study will receive about 12 sessions of arm training free of charge. Those in the inpatient and outpatient control study will also receive additional free training time to their customary care. Our prior research has shown improved hand, arm function, memory, focusing, decision making and reduced depression following intensive training in virtual reality.

For individuals with PD this research may uncover knowledge related to the influence of game characteristics on tremor magnitude and frequency. Further knowledge will be gained on potential use of Virtual Reality at treatment modality for this population.

o **Alternatives to Participation.** The sub-acute post-stroke subjects have the alternative to continue with customary rehabilitation without adding the experimental upper body training in virtual reality. The outpatient participants at Kessler Foundation have the alternative to continue their customary outpatient rehabilitation without adding the virtual reality therapy.

The individuals with PD participating in the pilot project at BCI/CCIT site have the alternative of not taking part in the study.

v. **Subject Identification, Recruitment and Consent/Assent**

o **Method of Subject Identification and Recruitment.**

1) Prospective post-stroke subjects will be identified based on their medical records kept at PowerBack Rehabilitation and at Kessler Foundation. Prospective volunteer healthy subjects for the BAC usability will be identified from the list of volunteers kept by BCI at CCIT. Prospective subjects sub-acute post-stroke will be given publicity fliers outlining their studies. Subjects interested to participate will be asked to contact [name] OT at PowerBack Rehabilitation or [name] MD at Kessler Foundation. For subjects admitted for short-term rehabilitation in PowerBack Rehabilitation, [name] OT reviews their intake medical data and will refer to the PI those that appear to be good candidates for the pilot feasibility study.

2) Prospective inpatient subjects at Kessler Foundation will be referred to [name] MD who will review their intake medical data.

o **Prospective subjects screening** will be done using different scripts at PowerBack (for BAC feasibility) and at Kessler Foundation (for RCT). For example the Kessler script will indicate randomization into an experimental or control group, and inability to guarantee where the prospective subject may be randomized to. The language describing the training will also be different on the two scripts. Those subjects that pass the screening, and wish to participate, will be told to contact [name] OT (feasibility) or [name] MD (controlled study) for follow up consent process.

Process of Consent. For participants post-stroke the consent process will be administered by [name], [name] OT (at PowerBack) and [name] MD and [name] MD (at Kessler Foundation) prior to their first clinical evaluation pre-therapy. During this process we will explain the experimental system, methods, and the objective of the study, the benefits and potential risks of participation, that the participation is entirely voluntary and free, and that the subject can drop out at any time without repercussions. Each prospective subject will be given 24 hours to make up his/her mind regarding participation. The caregivers of subjects participating in the randomized controlled study will also be consented, so they can provide feedback on recovery and increased ADL independence.

For individuals with PD the consent process will be conducted at BCI by [name] OT PhD

- o **Subject Capacity.** We will only include subjects that have the cognitive ability to give consent and who are English speakers. Subjects who do not speak English will not be included in the pool as we will not use translated publicity fliers.
- o **Subject/Representative Comprehension.** The consent process will be a dialogue in which patients and their caregivers will be given ample opportunity to ask questions, and be encouraged to participate. Only English-speaking subjects will be admitted in the study, in order to minimize the risk of misunderstandings. The person administering the consent process will make sure that the subjects understand what they will be expected to do during the training, and why, by asking potential subjects to explain to them what they have learned (reverse teaching).
- o **Debriefing Procedures.** An exit video interview will be conducted for all subjects training on the BAC. We will follow an established script to insure uniformity.
- o **Consent Forms.** Guidelines were followed in the new Consent Form to be used (attached to this application)
- o **Documentation of Consent.** Each Consent Form will have a subject ID, and will be in 3 copies. One copy will be given to the enrolled subject (or caregiver), 1 will be held by [name] and 1 by [name] OT, [name] OTor [name] MD, depending on which study component the subject was enrolled in (feasibility or controlled study). These will be hard-copy documents.
- o **Costs to the Subject.** Subjects will not incur costs due to participation in this study. Study costs will be paid by the grants received by BCI from NIH and from company internal resources. Parking is free at all clinical locations.
- o **Payment for Participation.** Participants in the BAC usability study at BCI/CCIT will receive \$25 for each session. At Kessler Foundation all 20 participants in the controlled study will receive \$25 for each evaluation session.

====End of document =====

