The feasibility pilot on individuals with PD at BCI Laboratories (CCIT) will determine technology acceptance and possible clinical benefit for better arms/hands motor control (reduced tremor), as well as focusing. Results from this pilot will be the basis for a follow up larger study.

The BAC usability component will take place at Bright Cloud International Laboratories, CCIT (North Brunswick, NJ). It will generate data on ease of use of the system, technical issues, and may lead to software improvements;

The BAC feasibility study will take place at PowerBack in Piscataway, NJ and will give initial indication of technology acceptance, as well as clinical benefit in terms of improved motor and cognitive function, reduced upper body pain, as well as diminished depression (feasibility) of short term residents at a Post-Acute facility.

The randomised controlled trials will take place at Kessler Foundation (West Orange, NJ). It will develop a new longitudinal therapy for elderly stroke survivors who are inpatients and then outpatients at a regional rehabilitation hospital, by adding BAC training to customary care for both inpatients and outpatients. Two systems will be used, improving continuity of care (one each for inpatient and outpatient settings).

This Protocol has **split oversight**, with the usability and feasibility components being overseen by WIRB, and the RCT component being overseen by Kessler IRB (KIRB).

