This study targets participants, who had suffered a stroke very recently, who may or may not have been diagnosed with mild cognitive impairments or dementia (including Alzheimer's disease). It is important to find out if these improvements can be obtained with the computer game-based integrative (motor-cognitive) bimanual rehabilitation developed by Bright Cloud International Corp, and if these gains transfer to daily activities. The study also aims at determining benefit of continuum care training on the BAC in addition to conventional rehabilitation for participants who are inpatients and then outpatients at a rehabilitation hospital and clinic.

Another component of the research project is a small pilot targeting individuals with Parkinson's disease. For them the project is going to:

- determine technology acceptance when using the BrightBrainer system;
- benefit to arms motor function and strengthening when playing BCI therapeutic games;
- benefit to reduction or tremor when playing games;
- cognitive benefits
- improvement in their wellbeing.

ii. Criteria for Subject Selection

For the BAC study on subjects early sub-acute post stroke

- o **Number of subjects:** We expect to enrol up to 50 subjects. Of these 4 will be healthy age-matched volunteers, 6 will be stroke survivors being treated at PowerBack, 20 stroke patients at Kessler Foundation, and 20 will be spouses/caregivers of subjects participating in the randomized control trials component of this study.
- o **Gender of Subjects.** Both male and female subjects will be equally enrolled. While the majority of the population is female, owing to the gender statistics for the age group targeted (>50 to 80 years old), since we will also recruit spouses/caregivers we expect an equal gender distribution. Due to their age, we do not anticipate any pregnant female to participate.

o **Age of Subjects.**

Age between 50 and 80. Subjects targeted are either: 1) healthy volunteers at BCI/CCIT location; inpatients in PowerBack Rehabilitation sub-acute post-stroke; 2) inpatients and then outpatients at a research hospital and its outpatient clinic at Kessler Foundation.

o **Racial and Ethnic Origin.**

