- pinch strength (pinch-meter)bimanual activities (Chedoke Inventory -9) [Barreca 2000]. The need to evaluate both UEs stems from the nature of BAC bimanual training and from our inclusion of subjects who may be bilaterally affected by their first CVA.

Emotional & Neuropsychological evaluations

- The neuropsychologist will perform the cognitive/emotive evaluations. We will assess
- emotive state (via the Beck Depression Inventory II)
 - verbal and visual attention (with the Neuropsychological Assessment Battery NAB)
 - processing speed (with the Trail Making Test A [Heaton 1991] - TMT)
 - verbal and visual learning and memory (with the Hopkins Verbal Learning Test, Revised (HVLTR) [Brandt 2001])
 - Brief Visuo-spatial Memory Test, Revised (BVMT-R) [Benedict 1997])
 - executive function with the Trail Making Test B (TMT-B) and the NAB Executive Functioning Module.

The initial evaluations will serve as baseline for all participants. Subsequent to the inpatient VR training, all participants will be evaluated again for cognitive and emotive state for indication of clinical benefit. Subjects who transition to home will be evaluated again at the start of their outpatient rehabilitation. All subjects will be evaluated again for cognitive and emotive state at the end of their outpatient therapy. For subjects who skip home rehabilitation and transition directly to outpatient training, the measures at discharged from inpatient rehabilitation will be considered as baseline for start of outpatient training. To minimize test learning effects we will use alternate test forms for NAB tests, as well as reliable change formulas for all other forms [Jacobsen and Truax, 1991].

Inpatient and outpatient experimental therapy for the control study at Kessler Foundation

All subjects, regardless of group randomisation, will continue their standard of care rehabilitation (physical therapy, occupational therapy, speech and language therapy and cognitive training). All subjects, regardless of randomization, will have the same duration of therapy. Specifically, subjects randomised in the control group will have an added duration of standard of care rehabilitation equal to the experimental group training duration on the BAC.

Experimental group

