10 subjects in the experimental group will be trained on the BAC system in addition to their standard of care intervention. Sessions will consist of a series of non-repeating custom and adaptable integrative games played while sitting at the robotic table. During the in-patient portion of the experimental therapy they will perform sessions every other day, for up to 3 weeks (12 sessions total). When transitioning to outpatient therapy, they will perform 2 to 3 sessions a week for 2 to 3 months.

Each experimental session will start with baseline measures of supported arm reach, pronation/supination range, finger extension and grasp strength. These measures will be done for the more affected arm during the initial 4 sessions, and for both arms thereafter, since therapy will progress to bimanual mode. The length of each session will increase with the progression of therapy, from 15 minutes in the first in-patient therapy session, to 30 minutes during the last in-patient session. Then during outpatient therapy portion, sessions will commence at 30 minutes duration and will progress to 45 minutes of actual game play.

The tilting angle of the robotic table will be used to modulate gravity loading on (typically) weak arms. If the subject is low-functioning the table may be tilted downwards to assist movement away from the trunk. Conversely, as the subject gets stronger, the table will be tilted upwards so to increase gravity loading. We plan on keeping the table flat during the inpatient sub-acute training and envisage this upwards tilting to occur in the outpatient component of the therapy.

Apart from lengthening the sessions and increasing gravity loading through robotic table tilting, we will increase session difficulty by incrementing the difficulty level of individual games. For example we may increase the number of face-down cards to be paired during the *Card Island* game (which trains short term visual and auditory memory), or increase the speed of the ball during *Breakout 3D* game (which trains hand-eye coordination, focusing, and dual tasking). In the outpatient portion, when attempting to lift the arm off the table, the weight of the forearm support will increase training difficulty further.

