In the motor domain the session will train endurance (by increasing the length of training), strength (by modulating gravity loading and lifting arm off table), motor control (by requiring patients to follow prescribed paths), and movement speed (by inducing more arm repetitions per minute).

In the cognitive domain the cognitive load will gradually be increased by moving from uni-manual play (need to control only one avatar) to bimanual play (simultaneous control of two avatars). This will train split attention, task sequencing and dual tasking, something problematic for the elderly.

Control group

10 subjects in the control group will receive their standard of care intervention during inpatient rehabilitation post CVA. To this we will add an equal duration of standard of care to the experimental therapy (progressing from 15 minutes/session in sessions 1-4 to 30 minutes during the last inpatient session). In the outpatient period they will have an added duration of customary therapy. The added therapy will progress from 30 minutes/session at start of outpatient therapy to 45 minutes/session at the end, matching the experimental group training duration on the BAC.

Control study Outcomes

Primary outcomes

The primary outcomes for both groups will be those outlines in the Feasibility Study component of the project. The main motor outcome measure will be the FMA UE score, and success will be a group average score increase of 10 points or more, compared to baseline. The main outcome for the cognitive domain will be executive function improvement measured by Trail Making Test B (TMT-B) and the NAB Executive Functioning Module.

Secondary outcomes

The secondary outcomes for both groups will be those outlined in the Feasibility Study component of the project,

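### The randomised study identifies only BAC versus equal extra conventional therapy; it cannot separate natural recovery, and its stated aim names no comparator

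*Protocol*

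**What the plan says.** **Aim.** Protocol section i (Why is this study being done?) aims at "determining benefit of continuum care training on the BAC in addition to conventional rehabilitation". Section I (Purpose of the study and background) says the randomised study will develop a new therapy "by adding BAC training to customary care for both inpatients and outpatients". Neither sentence says what BAC is compared with.

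**Arms.** Under Experimental group: "10 subjects in the experimental group will be trained on the BAC system in addition to their standard of care intervention". The paragraph introducing inpatient and outpatient therapy at Kessler says that the "control group will have an added duration of standard of care rehabilitation equal to the experimental group training duration on the BAC". The Control group section repeats this for the inpatient period ("To this we will add an equal duration of standard of care to the experimental therapy") and for the outpatient period ("matching the experimental group training duration on the BAC").

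**Promised interpretation.** At the end of Control study Outcomes, curves of the evaluation variables before and after inpatient and outpatient therapy are to "elucidate what gains are due to natural recovery and what gains may be attributes to training on the BAC".

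**Success and analysis.** Control study Outcomes defines motor success as a group mean FMA rise of at least 10 points from baseline. Data Analysis and Data Monitoring describes a repeated measures ANOVA of pre-training against post-training results.

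**The concern.** The interpretation promised for the recovery curves needs something the design lacks. To say how much gain is natural recovery, some participants would have to be observed without therapy. Here everyone continues standard care, and controls receive more of it. The control curve therefore combines natural recovery, standard care and the added therapy. Reading it as natural recovery would overstate recovery.

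The aim has a milder fault. Because it names no comparator, it can be read as the benefit of BAC over customary care alone. The Background section makes that reading easier: in the precursor pilot it describes, controls had only customary care. The randomised study has no such group.

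What is at stake is the conclusion the trial may draw. A rise from baseline in the BAC arm contains recovery and usual therapy, and the success criterion and pre/post wording would let all of it be credited to BAC.

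**Working it through.** **What each arm contains.** Let N be natural recovery, S standard care, X the added conventional therapy and B the BAC training, each as mean FMA gain. Additivity is a simplifying assumption.

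- Experimental arm: N + S + B
- Control arm: N + S + X
- Difference: (N + S + B) − (N + S + X) = B − X

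There are two arm means and four unknowns. A matrix-rank check confirms that B − X is estimable and that B, X, N and N + S are not.

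**Would another control arm change this?** With a standard-care-only arm (mean N + S), B becomes estimable, since (N + S + B) − (N + S) = B. N alone still does not, because that arm is treated too. So natural recovery is inseparable because every arm receives therapy, not because controls receive extra therapy.

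**Does the gap between inpatient and outpatient therapy help?** The section on standardised evaluations for the control study gives the extra pre-outpatient evaluation only to patients who go through home rehabilitation. That subset is not formed by randomisation and is still in rehabilitation. Change over the gap is therefore not N, and it is not seen in everyone.

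**How much therapy is in X?** The protocol gives no total, so I bound it.

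- *Inpatient.* There are up to 12 sessions (Experimental group). The Control group section fixes 15 minutes for sessions 1 to 4 and 30 minutes for the last, and leaves sessions 5 to 11 open. With a progression that never decreases:
  - lowest: 4×15 + 7×15 + 30 = 195 minutes
  - highest: 4×15 + 7×30 + 30 = 300 minutes
- *Outpatient.* There are 2 to 3 sessions a week for 2 to 3 months, starting at 30 minutes and ending at 45. Taking 2 to 3 months as 8 to 13 weeks (my assumption):
  - lowest: 8×2×30 = 480 minutes (8 h)
  - highest: 13×3×45 = 1,755 minutes (29.25 h)
- *Total.* 195 + 480 = 675 minutes to 300 + 1,755 = 2,055 minutes, or about 11 to 34 hours. These are outer bounds, since session length moves from 30 to 45 minutes rather than staying at either.

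**What B − X can look like.** The protocol gives no effect values, so these are purely illustrative. If B = 5 and X = 3 FMA points, the trial estimates 5 − 3 = 2. If B = X, it estimates 0, whatever B is.

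**What the success criterion would say.** If both arms rise by 10 points from baseline, each meets the criterion, while the between-arm difference is 10 − 10 = 0. The criterion cannot tell BAC from recovery plus therapy.

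**The case against.** The strongest reply is that the design is sound. A control matched for therapy time removes dose as an explanation, and natural recovery, being common to randomised arms, cancels in expectation from the difference. The gain attributable to BAC relative to equal conventional time is therefore validly estimated. This stands. A reader might infer that the trial can say nothing about what BAC contributes; the documents do not support that.

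Second, the two aim sentences can be read as describing the experimental regimen, which does add BAC to standard care. This also stands. A reader might infer that the aim contradicts the design, but neither sentence claims a comparison with customary care alone. The fault is an unnamed comparator.

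Third, the recovery-curve statement is hedged and concerns an additional outcome, not the primary one. That limits its weight. It does not rescue the natural-recovery half, which no contrast in this trial can supply.

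Finally, a reader might infer that the main danger is a false null, with equal efficacy reported as no benefit from adding BAC. No section sets such a rule. Under the written within-group criterion, equal gains of 10 points would count as success, so the documented risk is over-crediting BAC.

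**Conclusion.** The point holds as a mismatch between stated interpretation and design, not as a defect of the design. The trial identifies BAC versus the same minutes of added conventional therapy, both on top of standard care. The claim to show which gains are natural recovery is wrong as written, because every participant is treated. The benefit over customary care alone, which the aim could be taken to mean, cannot be estimated.

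The difference between the two questions is not negligible: controls receive roughly 195 to 300 added inpatient minutes and about 8 to 29 added outpatient hours. The inpatient range assumes all 12 sessions and a non-decreasing progression; the outpatient range assumes 8 to 13 weeks. How far B − X departs from B in FMA points cannot be sized from the protocol. The non-identifiability of natural recovery needs no numerical assumption, since it follows from the absence of an untreated arm.

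A statistical analysis plan, which is not at hand, may specify the between-arm analysis. It could not make natural recovery identifiable.

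**What to change.** Keep the arms, the sample size and the assessments.

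1. In Control study Outcomes, delete the statement that the curves will show which gains are due to natural recovery. Say instead that the curves describe change in each arm, and that only the between-arm difference in change is attributed to BAC.
2. In sections I and i, state the question of the randomised study as BAC training versus an equal duration of added conventional therapy, both on top of standard care.
3. In Control study Outcomes and Data Analysis and Data Monitoring, say that any conclusion about BAC rests on the between-arm contrast in change. The 10-point rise from baseline may stay as a description of each group, but not as evidence of a BAC effect.

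The cost is an amendment of wording and a narrower claim. No participant, visit or procedure changes. If the sponsor wants the benefit over customary care alone, that needs a standard-care-only group, which is a different trial; even that would not isolate natural recovery.
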